5.2. Other Baseline Characteristics

In addition to the randomization stratification factors listed in Section 3.3, the following demographic and baseline characteristics will be summarized by treatment group for the overall population:

- Age and Age group (≥ 65 years or < 65 years)
- Gender (male or female)
- Race
- Region
- Ethnicity (Hispanic/Latino, not Hispanic/Latino, or not permitted)
- Height
- Weight
- BMI
- Clinician symptom severity score ([Appendix 3](#), Form A, row 1, box 2)
- Health care provider global ratings ([Appendix 3](#), Form A, row 1, box 1)
- Total score of Lee Symptom Scale
- Skin domain score of the Lee Symptom Scale
- Mouth domain score of the Lee Symptom Scale
- Eyes domain score of the Lee Symptom Scale

5.3. Medical History

General medical history data will be collected at screening and listed but not coded.

6. EFFICACY ANALYSES

6.1. Definition of the Primary Efficacy Endpoint

The primary endpoint is BORR by 24 weeks, defined as the proportion of subjects who achieve a complete or partial overall response (CR or PR) as assessed by the NCAA (Appendix 3) within 24 weeks, in the setting of add-on therapy to systemic corticosteroids as part of first-line therapy for cGVHD.

At each assessment time point, organ-specific responses will be determined according to Appendix 2. An overall time point response across all involved organs will then be determined according to Table 3. The best overall response across all time points up to 24 weeks will be used to calculate BORR by 24 weeks.

Table 3. Criteria for time point response determination

Response Category	Response Criteria
Complete response (CR)	Resolution of all cGVHD manifestations in each organ or site as described in the NCAA organ response determination table
Partial response (PR)	Improvement of at least 1 organ or site, without progression in any other organ or site as described in the NCAA organ response determination table.
Stable disease (SD)	Neither sufficient improvement to qualify for a PR nor sufficient decline to qualify for a PD
Progressive disease (PD)* * A flare is defined as acute worsening of signs and symptoms in any organ or site that occurs at least 4 weeks after PR/CR is achieved, which lasts ≤ 4 weeks.	
 • Worsening of signs and symptoms in any organ or site as described in the NCAA organ response determination table, taking the baseline as reference. OR • Increase in systemic corticosteroid dose to ≥ baseline dose (1 mg/kg/day) OR • Initiation of systemic immunosuppressive therapy other than systemic corticosteroids

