PPD

Test Product, Dose, and Mode of Administration:

Treatment Arm 1: ENTO 400 mg twice daily: 2 X 200 mg tablets twice daily, for subjects currently on proton pump inhibitors (PPI)*

Treatment Arm 2: Placebo-to-match (PTM) twice daily

Both treatment arms will be administered orally without food (in a fasted state) for 48 weeks.

*For subjects **NOT** currently taking a PPI, the dose will be adjusted to ENTO 200 mg twice daily: 1 X 200 mg tablet orally twice daily without food (in a fasted state) for 48 weeks.

Reference Therapy, Dose, and Mode of Administration:

Systemic corticosteroids at a dose and route consistent with first-line therapy for newly diagnosed cGVHD.

Systemic corticosteroids will be administered per provided treatment schema.

Criteria for Evaluation:

Safety:

Safety evaluations include documentation of AEs, physical examination, vital signs, ECGs, and clinical laboratory evaluations.

Efficacy:

The primary endpoint is BORR by 24 weeks, as assessed by the NCAA, in the setting of add-on therapy to systemic corticosteroids as part of first-line therapy for cGVHD.

The key secondary endpoints are:

- Change from Baseline in the skin domain of the LSS at 24 weeks
- Change from Baseline in the mouth domain of the LSS at 24 weeks
- Change from Baseline in the eyes domain of LSS at 24 weeks
- Change from Baseline in the total score of the LSS at 24 weeks

Other secondary endpoints include:

- DOR
- Proportion of subjects who achieve at least 50% reduction in systemic corticosteroid dose relative to baseline
- Proportion of subjects who initiate second-line therapy for cGVHD
- Failure-free-survival (FFS)
- Safety and tolerability of ENTO

Exploratory endpoints of this study include:

P	[Redacted]
P	[Redacted]
D	[Redacted]
[Redacted]	[Redacted]
[Redacted]	[Redacted]
[Redacted]	[Redacted]

Pharmacokinetics: PK blood sampling will occur at Weeks 2 through Week 48 and then every 12 weeks thereafter.

Statistical Methods:

The primary endpoint of BORR by 24 weeks is defined as the proportion of subjects who achieve a complete or partial response (CR or PR) within 24 weeks, as assessed by the NCAA. A CR is achieved when all signs and symptoms of cGVHD have resolved. A PR is achieved when an objective response is observed in any organ system without progression in another organ system, and no additional systemic therapy is needed.

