3.4. Discontinuation Criteria

Subject participation may be discontinued in the following instances:

- Intercurrent illness that would, in the judgment of the investigator, affect assessments of clinical status to a significant degree.
- Unacceptable toxicity, or toxicity that, in the judgment of the investigator, compromises the ability to continue study-specific procedures or is considered to not be in the subject's best interest
- Relapse of primary disease
- Severity of cGVHD requiring therapy that is not allowed as concomitant therapy on study (for example JAK inhibitor/BTK inhibitor /mTOR inhibitors/ any cell depletion agent/ phototherapy)
- Subject request to discontinue for any reason
- Subject noncompliance
- Pregnancy during the study; refer to [Appendix 8](#)
- Discontinuation of the study at the request of Gilead, a regulatory agency or an Institutional Review Board or Independent Ethics Committee (IRB/IEC)

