6.5. Post-treatment Assessments

6.5.1. Unscheduled Visit

A subject should attend an unscheduled visit if requested by the Sponsor or the investigator. The assessments performed are at the investigator's discretion.

For subjects that initiate second line therapy during the study, every attempt should be made to collect the NCAA and LSS at an unscheduled visit and to keep the subject in the study and study related follow-up procedures should be continued.

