6.5.2. Early Study Drug Discontinuation (ESDD)

If the subject discontinues study drug prior to the end of study, the subject will be asked to return to the clinic within 72 hours of stopping study drug for the Early Study Drug Discontinuation Visit. The subject will be asked to continue attending the schedule study visits through Week 48. Subjects who ESDD will not be eligible for the OLE phase of the study.

At the ESDD visit, any evaluations showing abnormal results indicating that there is a possible or probable causal relationship with the study drug, should be repeated weekly (or as often as deemed prudent by the investigator) until the abnormality is resolved, returns to baseline, or is otherwise explained.

Evaluation listed in [Table 6-1](#) will be completed at the ESDD visit.

The following will be conducted at the ESDD: review of adverse events (AEs) and changes in concomitant medications, vital signs (including weight), complete physical exam, primary malignancy assessment (if applicable), blood for hematology, chemistry, metabolic panel, selected biomarkers and urine for: pregnancy test (if applicable), and urinalysis. The NCAA and LSS will be assessed.

PFTs will be required at ESDD: spirometry with bronchodilator and diffusing capacity of the lungs for carbon monoxide (DLCO).

6.6. 30 Day Follow-Up Visit

Subjects who complete through Week 48 visit and who do not wish to participate in the OLE phase of the study will return to the clinic 30 days after the completion of study drug for the 30-Day follow-up visit. Subjects who complete the OLE will return to the clinic 30 days after the completion of study drug for the 30-Day follow-up visit

Subjects who permanently discontinue study drug and refuse to continue in the study will be asked to return to the clinic 30 days after the completion of the ESDD visit for the 30-Day follow-up visit.

For the purpose of scheduling a 30-Day follow-up visit, a ± 5 days window may be used. [Table 6-1](#) lists all procedures to be completed at the 30-Day Follow-up visit.

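### The Week 24 best-response rule in SAP 6.1 can credit a response first reached after new systemic immunosuppression, which the protocol synopsis excludes for PR

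*SAP*

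**What the plan says.** SAP 6.1 determines a response at each time point from Table 3 and then combines the visits: "The best overall response across all time points up to 24 weeks will be used to calculate BORR by 24 weeks". Protocol 8.1.2 contains the same sentence and applies its own Table 8-1.

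Two rows of Table 3 matter here, and Table 8-1 agrees with it on both:

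- PR is "Improvement of at least 1 organ or site, without progression in any other organ or site". The only bar is organ progression.
- PD includes "Initiation of systemic immunosuppressive therapy other than systemic corticosteroids". A further PD criterion begins "Increase in systemic corticosteroid dose to" and sets the threshold at the baseline dose.

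The protocol synopsis (Statistical Methods) is stricter on PR. It requires improvement "without progression in another organ system, and no additional systemic therapy is needed".

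On follow-up after second-line therapy starts, protocol 6.5.1 says "every attempt should be made to collect the NCAA and LSS at an unscheduled visit and to keep the subject in the study". For subjects who stop study drug, protocol 6.5.2 says "The subject will be asked to continue attending the schedule study visits through Week 48". Against this, protocol 3.4 allows participation to end for "Severity of cGVHD requiring therapy that is not allowed as concomitant therapy on study".

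The only data-handling rule in SAP 6.3 concerns missing questionnaires and missing domain scores.

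**The concern.** When the best of all visits is taken, a PD at one visit does not cancel a PR at a later one. The new-therapy criterion is worded as an event, the start of a drug. Unless the plan says that this PD persists, a later visit can be rated on organ scores alone, and the PR row contains nothing to stop it. The response would then be attributed to first-line therapy although it followed a second-line agent.

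This is the primary endpoint. Two programmers working from the same data could reach different responder counts, and one of those counts would contradict the synopsis. If rescued subjects improve at similar rates in both arms, the arm with more non-responders gains more responders and the treatment difference shrinks.

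**Working it through.** **Does the text allow it?** Take a subject with no response who starts a second-line agent at Week 8 and first improves in one organ at Week 16.

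- Data: the NCAA is scheduled at Weeks 4, 8, 12, 16, 20 and 24 and at the start of second-line therapy (protocol Table 6-1). Protocol 6.5.1 and 6.5.2 ask for continued follow-up, so a Week 16 rating can exist.
- SAP Table 3, read visit by visit: PD at Week 8, PR at Week 16, best response PR, so a responder.
- Synopsis: additional systemic therapy was needed, so not a PR.

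The two readings disagree, and no visible text in SAP 6.1, SAP 6.3 or protocol 8.1.2 settles it. Non-responder imputation appears in the protocol's abbreviation list but is not applied in the visible text.

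**The plan's own figure.** The sample size sections (protocol 8.9, SAP 1.3) give placebo 50%, a 30-point improvement, two-sided 0.05, Fisher's exact test, 40 per arm and 75% power. Exact enumeration over both binomials gives 74.9%, so the figure is reproduced. Dropout of 20% gives 40/0.8 = 50 per arm, where power is 85.3%.

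**Illustration.** Let q be the share of non-responders rescued and r the share of those who then improve, both by Week 24 and with a scored NCAA. Assume 80% and 50% are the rates before rescue, and that q and r are equal in both arms:

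- ENTO: 0.8 + 0.2·q·r
- Placebo: 0.5 + 0.5·q·r

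The value r = 0.5 is an assumption. It lies within the 20–70% initial second-line response quoted in protocol 1.1.1. The documents give no value for q.

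| q (r = 0.5) | ENTO / placebo | Difference in points, Wald 95% CI at 50 per arm | Fisher power, 40 / 50 per arm |
|---|---|---|---|
| 0% | 80.0 / 50.0 | 30.0 (12.3 to 47.7) | 74.9% / 85.3% |
| 10% | 81.0 / 52.5 | 28.5 (10.9 to 46.1) | 71.1% / 82.2% |
| 30% | 83.0 / 57.5 | 25.5 (8.3 to 42.7) | 63.4% / 75.2% |
| 40% | 84.0 / 60.0 | 24.0 (7.0 to 41.0) | 59.4% / 71.3% |

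For the 30% row, q·r = 0.15. Credited subjects per 50 are 50 × 0.2 × 0.15 = 1.5 on ENTO and 50 × 0.5 × 0.15 = 3.75 on placebo. Each credited subject moves an arm's BORR by 1/50 = 2 points.

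**Direction.** With credited shares of non-responders x1 (ENTO) and x0 (placebo), the difference is 0.30 + 0.2·x1 − 0.5·x0. It falls below 0.30 only if x0 > 0.4·x1. Examples:

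- x1 = 15%, x0 = 6%: 30.0 points
- x1 = 15%, x0 = 0%: 33.0 points
- x1 = 0%, x0 = 15%: 22.5 points

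No futility figure is given. The interim set admits early responders (SAP 3.1.1), so simple binomial counts do not describe it. A predictive probability of 30% or less leads to a DMC review under a non-binding rule (SAP 2.2).

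**The case against.** The strongest reply is that PD can be read as lasting. A subject who has started another agent since baseline still meets that criterion at Week 16, and both the first-line framing in SAP 6.1 and the synopsis point to non-response. That is probably the intent, but the tables do not say so, and the count depends on which reading is programmed.

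Several limits stand:

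- SAP 6.6 is redacted, and a rule there cannot be excluded. The point concerns 6.1 and 6.3 as they read.
- SAP 3.5 drops formal comparisons after early termination. The power figures therefore describe the design and not a live test. SAP 6.3 also names CMH rather than Fisher, although it still lists that test and a BORR difference with its CI.
- The affected group is narrow: no response before rescue, kept in the study despite protocol 3.4, then improved and scored by Week 24. Its size is not in the documents, and neither is the number enrolled at termination.
- The direction of the effect is not established.

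A further objection is that changing the responder rule after an unblinded interim risks a data-informed choice. This would weigh heavily against a new rule. It weighs less here because, for PR, the change restores a condition already in the synopsis, and both counts would be reported.

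Finally, the two tables are not identical throughout. Worsening is judged against baseline in SAP Table 3 and against current best response in protocol Table 8-1. They agree on the elements at issue here.

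**Conclusion.** The concern holds. The SAP's visit-level tables and best-response rule allow a PR reached after second-line therapy to count in BORR, and the synopsis does not. This is a conflict within the definition of the primary endpoint and should be corrected.

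The practical size is uncertain. Under equal rescue of 10% to 40% of non-responders with half improving, the planned 30-point difference would be reported as 28.5 to 24.0 points. Unequal rescue could enlarge or shrink it. These figures rest on planned sample sizes, on 80% and 50% being rates before rescue, and on assumed rescue and improvement rates. What is now exposed is the reported BORR by arm, the difference and its CI.

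**What to change.** In SAP 6.1 and 6.3:

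1. Count toward BORR only a CR or PR documented before the first systemic immunosuppressant, other than corticosteroids, newly started after Day 1. Baseline calcineurin inhibitor or MMF use is not a new start. Responses reached earlier are kept. The synopsis attaches its condition to PR only, so state explicitly that the rule also applies to CR.
2. Add the synopsis condition to the PR row of Table 3.
3. State whether PD from a corticosteroid increase to the baseline dose or above is handled in the same way for BORR. The documents leave this open.
4. Report BORR under the all-visits rule as a sensitivity analysis, with the number of subjects per arm whose first response came after new systemic therapy. If that number is zero in both arms, BORR is unaffected.

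The cost is SAP wording and reprogramming on data already collected: the scheduled NCAA visits, the NCAA at the start of second-line therapy, and dated concomitant medications. Reported response rates may be slightly lower in both arms. Because the change follows the interim, record its date and its basis in the synopsis.

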5.4. Prior and Concomitant Medications

Systemic corticosteroids are required at study entry. Administration and taper recommendations are below:

- **Prednisone:** administered initially as a single early morning dose of 1.0 mg/kg/day [or equivalent (Adults: maximum dose 100 mg)]. If due to formulation of prednisone tablets 1.0 mg/kg/day is not possible, we allow a range of 0.90 to 1.10 mg/kg/day.
- Prednisone therapy continues at the initial dose until there is objective evidence of improvement in manifestations of cGVHD (ie, a PR or better), minimum of 14 days of co-administration of ENTO/Placebo and prednisone.
- The initial taper of prednisone from the starting dose of 1.0 mg/kg/day (or equivalent) may be attempted 14 days after co-administration with ENTO/Placebo if there is evidence of improvement in cGVHD
- If exacerbation or recurrence of cGVHD is evident at any step of the taper, the dose of prednisone should be increased promptly by 2 levels, with daily administration for 2 to 4 weeks, followed by resumption of alternate-day administration. Please see [Table 5-1](#) for tapering.

Table 5-1. Tapering of Prednisone after reaching PR/CR

Week	Dose, mg/kg body weight (example for 80kg patient in mg)
0	1.0 once a day (80)
1-3	1.0/0.5 (to begin within 1 week after objective improvement, alternating days) (80/40/80)
4-5	0.5 once a day (40)
6-7	0.5 every other day (40/0/40)
8-9	0.25 every other day (20/0/20)
10	0.1 every other day (10/0/10) with ultimate goal of complete discontinuation of Prednisone

- Inhaled and topical steroids (eg, Budesonide/ Beclomethasone) are not considered second-line therapy and are permitted throughout the duration of the study. Addition of the aforementioned agents will be recorded in the eCRF for posterior analysis.
- Local organ-specific treatment (eg, eye drops) will be recorded in the eCRF and assessment of response after local organ-specific treatment will be based on the NCAA.

Co- Administration of ENTO with Other Classes of Immunosuppresant Agents during OLE:

- During the extension phase (post 96 weeks of study) or OLE, for patients who are eligible to remain on study, the maximum period of co-administration of ENTO with Cyclosporine, Tacrolimus or MMF should not exceed 3 months. The sponsor envisions that if the subject has stable or refractory disease, they should be transitioned to other forms of therapies within this 3 month period.

Disallowed Medications:

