8.1.2. Primary Endpoint

The primary endpoint is BORR by 24 weeks, defined as the proportion of subjects who achieve a complete or partial overall response (CR or PR) as assessed by the NCAA within 24 weeks, in the setting of add-on therapy to systemic corticosteroids as part of first-line therapy for cGVHD.

At each assessment time point, organ-specific responses will be determined according to [Appendix 4](#). An overall time point response across all involved organs will then be determined according to [Table 8-1](#). The best overall response across all time points up to 24 weeks will be used to calculate BORR by 24 weeks.

Table 8-1. Criteria for time point response determination

Response Category	Response Criteria
Complete response (CR)	Resolution of all cGVHD manifestations in each organ or site as described in the NCAA organ response determination table
Partial response (PR)	Improvement of at least 1 organ or site, without progression in any other organ or site as described in the NCAA organ response determination table.
Stable disease (SD)	Neither sufficient improvement to qualify for a PR nor sufficient decline to qualify for a PD
Progressive disease (PD)	
 • Worsening of signs and symptoms in any organ or site as described in the NCAA organ response determination table, taking the current best overall response as reference that is not a flare. A flare is defined as acute worsening of signs and symptoms in any organ or site that occurs at least 4 weeks after PR/CR is achieved, which lasts ≤ 4 weeks. 
OR
 
 • Increase in systemic corticosteroid dose to \geq baseline dose (1 mg/kg/day) 
OR
 
 • Initiation of systemic immunosuppressive therapy other than systemic corticosteroids

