2.2. Interim Analysis

The DMC is primarily responsible for reviewing safety data. Efficacy data will be reviewed only during the formal interim futility analysis after approximately 50% of subjects have been on study for 24 weeks, or have discontinued the study before 24 weeks, or have achieved a response prior to reaching 24 weeks. A non-binding futility rule will be implemented which is based on the predictive probability of success.

The predictive probability of success is defined as the probability of achieving statistical significance (two sided p-value < 0.05) and a $\geq 30\%$ difference in the BORR between the ENTO and placebo group at the study completion given the data observed at the interim.

If the predictive probability of success is $> 30\%$, the study will continue. If the predictive probability of success is $\leq 30\%$, the totality of the data including the DOR, response rate at Week 24, and safety data will be reviewed by the DMC to make a thorough risk-benefit assessment. The VP of Clinical Research and the VP of Biometrics at Gilead may review the interim futility analysis results to make subsequent decisions based on the DMC recommendations.

A 2-sided alpha of 0.001 will be allocated to this interim futility analysis; following the Haybittle-Peto approach, the week 24 analysis alpha level will be 0.05 (2-sided).

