6.4. Secondary Efficacy Endpoints

6.4.1. Definition of Secondary Efficacy Endpoints

The key secondary endpoints are:

- Change from baseline in the skin domain of the LSS at 24 weeks
- Change from baseline in the mouth domain of the LSS at 24 weeks
- Change from baseline in the eyes domain of the LSS at 24 weeks
- Change from baseline in the total score of the LSS at 24 Weeks

Other secondary endpoints include:

- Duration of response, defined as the time from the documentation of BORR to the documentation of PD as defined in [Table 3](#). Note that a flare does *not* constitute an end to response. A sensitivity analysis for DOR could consider a flare does constitute an end to response.
- Proportion of subjects who ever achieve at least 50% reduction in systemic corticosteroid dose relative to baseline, where % reduction is calculated as (systemic corticosteroid dose at 24 weeks – baseline systemic corticosteroid dose) / baseline systemic corticosteroid dose.
- Proportion of subjects who initiate second-line therapy for cGVHD, defined as receiving any therapy besides systemic corticosteroids or study drug for the treatment of cGVHD. Inhaled and topical steroids are not considered second-line therapy.
- Failure-free survival (FFS), defined as the time from randomization to the earliest of first documentation of systemic therapy change, non-relapse mortality, or recurrent malignancy

- Safety and tolerability of ENTO

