6.4.2. Analysis Methods for Secondary Efficacy Endpoints

The key secondary endpoints will be analyzed using a two sample z-test at week 24.

Other secondary endpoints will be analyzed as follows:

DOR and FFS will be analyzed using the Kaplan-Meier (KM) method and stratified logrank test. Kaplan-Meier summary statistics (median, 95% CI for median, and 25th, 75th percentiles) and number and percentage of events will be presented by treatment group. A stratified Cox proportional hazards model will be used to estimate the hazard ratio and corresponding 95% CI. A KM survival plot will also be provided. Data for subjects who do not experience an event will be censored at the date of last visit. DOR will be analyzed only on subjects who responded.

Proportion of subjects with at least 50% reduction in systemic corticosteroid dose relative to baseline and proportion of subjects who initiated a second-line therapy for cGVHD will be analyzed similarly to the primary endpoint.

Line plot of change from baseline in each domain and total of LSS will be done.

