- 16) For subjects receiving tacrolimus, cyclosporine or MMF the blood levels of tacrolimus, cyclosporine or the active metabolite of MMF (MPA) will be monitored at baseline/Day 1 (prior to starting ENTO or PTM), on day 2 or day 3 and day 6 or day 7 after initiating ENTO or PTM, and at the end of Week 2 and Week 50 study visit. Beyond these time points, concentration monitoring for tacrolimus, cyclosporine and MPA should follow the treating institutions protocol and therapeutic range for monitoring these medicines
- 17) Assessments may include but are not limited to: cytokines, cell subset analysis, pathway markers, and/or other B-cell activating factor, B-cell function, immunoglobulin levels, and/or antigen-specific B cell response. Timepoints may differ depending on the specific biomarker and will be outlined in the Central Lab Manual.
- 18) At visit 2, 30, 42 and (OLE visit 50) drug accountability only, study drug will not be dispensed at these visits
- 19) Will include the following: systemic corticosteroid dose, other immunosuppressive, antimicrobials, PPI
- 19) PFTs will include spirometry with bronchodilator, and diffusing capacity of the lungs for carbon monoxide (DLCO). PFTs will be done at ESDD, if ESDD visit greater than 12 weeks from Baseline. Any PFT done within 30 days prior to randomization can be used in lieu of Screening PFT.

Appendix 2. For Baseline + Subsequent Visits: Response Determination for the NIH cGVHD Activity Assessment (NCAA)

Organ	Complete Response	Partial Response	Progression
Skin	NIH Skin Score 0 after previous involvement	Decrease in NIH Skin Score by 1 or more points	Increase in NIH Skin Score by 1 or more points, except 0 to 1
Eyes	NIH Eye Score 0 after previous involvement	Decrease in NIH Eye Score by 1 or more points	Increase in NIH Eye Score by 1 or more points, except 0 to 1
Mouth	NIH Modified OMRS 0 after previous involvement	Decrease in NIH Modified OMRS of 2 or more points	Increase in NIH Modified OMRS of 2 or more points
Esophagus	NIH Esophagus Score 0 after previous involvement	Decrease in NIH Esophagus Score by 1 or more points	Increase in NIH Esophagus Score by 1 or more points, except 0 to 1
Upper GI	NIH Upper GI Score 0 after previous involvement	Decrease in NIH Upper GI Score by 1 or more points	Increase in NIH Upper GI Score by 1 or more points, except 0 to 1

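### For duration of response, the SAP measures organ progression from baseline where the protocol measures it from best response, so a relapse back to baseline does not end the response

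*SAP*

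**What the plan says.** Protocol Section 8.1.2, Table 8-1, defines organ-based PD as worsening judged "taking the current best overall response as reference that is not a flare". SAP Section 6.1, Table 3, replaces that reference: "Worsening of signs and symptoms in any organ or site as described in the NCAA organ response determination table, taking the baseline as reference". Table 3 keeps the definition of a flare (worsening at least 4 weeks after PR/CR that lasts 4 weeks or less) as a note, but its PD criterion no longer contains the exclusion.

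The two therapy-based PD criteria are the same in both tables: systemic corticosteroid raised to at least the baseline dose (1 mg/kg/day), and a new systemic immunosuppressant.

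SAP Section 6.4.1 gives "Duration of response, defined as the time from the documentation of BORR to the documentation of PD", pointing to Table 3; Protocol Section 8.1.3 points to Table 8-1. Neither document has a separate loss-of-response event. SAP 6.4.1 says that a flare does not end response and adds: "A sensitivity analysis for DOR could consider a flare does constitute an end to response". SAP Section 6.4.2 specifies Kaplan-Meier, a stratified log-rank test and a stratified Cox model for DOR in responders, with "Data for subjects who do not experience an event will be censored at the date of last visit".

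**The concern.** One endpoint name carries two different end events. A subject whose skin score goes 2, 0, 2 has lost the response. Under the protocol this is PD unless it is a flare. Under the SAP the change from baseline is zero, so the visit is stable disease and DOR continues.

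DOR is a secondary endpoint with its own analysis. SAP Section 2.2 also makes it part of the evidence when the predictive probability of success is 30% or less: "the totality of the data including the DOR, response rate at Week 24, and safety data will be reviewed by the DMC". Failure-free survival, second-line therapy and steroid reduction also bear on durability, but they register therapy changes, death or malignancy, not organ relapse. If organ relapse back to baseline is invisible to DOR, no other listed secondary endpoint records it directly.

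**Working it through.** **Design figure.** The documents state no numerical assumption for DOR. Their only design figure concerns BORR: 40 per arm, 50% versus 80%, Fisher's exact test at two-sided 0.05. It reproduces (power 0.749 against 75% stated; 80/(1 − 0.20) = 100 subjects), and this point does not depend on it.

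**Inputs.** The organ thresholds are the same in SAP Appendix 2 and Protocol Appendix 4. For skin: "Increase in NIH Skin Score by 1 or more points, except 0 to 1". Eyes, esophagus, upper GI and lower GI follow the same rule. For the mouth (OMRS, 0 to 12), PR is a fall of 2 or more and progression a rise of 2 or more, with no exemption.

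**0 to 3 organs.** Let b be the baseline score, r < b the score at the visit taken as best response, and f > r a later score. PD is a rise of at least 1, except 0 to 1, measured from r (protocol) or from b (SAP).

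| Baseline b | Worsening paths | PD, protocol | PD, SAP |
|---|---|---|---|
| 1 | 3 | 2 | 2 |
| 2 | 5 | 4 | 2 |
| 3 | 6 | 5 | 0 |
| Total | 14 | 11 | 4 |

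Seven paths are PD only under the protocol, none only under the SAP, and three under neither. For exact return to baseline (f = b) there are 6 paths: 5 are PD under the protocol and 0 under the SAP. The exception is 1, 0, 1, exempt under both. An organ of this type scored 3 at baseline can never show organ PD under the SAP, because the scale stops at 3. Lungs and joints differ, since they also have %FEV1 and P-ROM.

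**Mouth.** For return to baseline after a fall of 2 or more there are 1 + 2 + … + 11 = 66 paths: 66 PD under the protocol, 0 under the SAP. Over all later worsening (572 paths) the counts are 506 and 165. A reverse case exists: an OMRS of 4 at baseline that stands at 5 when another organ responds is PD at 6 under the SAP but only at 7 under the protocol.

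**Steroid criterion as a back-up.** Protocol Section 5.4 says that on exacerbation during taper "the dose of prednisone should be increased promptly by 2 levels, with daily administration for 2 to 4 weeks". Moving each Table 5-1 step up two levels, capped at 1.0 mg/kg daily:

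| Step (weeks) | Two levels up | Reaches 1 mg/kg/day? |
|---|---|---|
| 1-3 | 1.0 daily (cap) | Yes |
| 4-5 | 1.0 daily | Yes |
| 6-7 | alternating 1.0/0.5 | Depends on reading |
| 8-9 | 0.5 daily | No |
| 10 | at most 0.5 | No |

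The criterion is met at 2 of 5 steps for certain and 3 at most.

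**Flares.** If flare worsening is read from the PR/CR state, a three-week return to baseline would end response in the SAP's sensitivity analysis. A return lasting more than 4 weeks is neither a flare nor PD, so on organ criteria it would end response in neither analysis.

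**Illustration of size, by assumption only.** Let m be the share of protocol PD events missed, with exponential DOR.

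- If missed relapses stay at risk and never become PD, S(t) = m + (1 − m)exp(−kt), and the median is multiplied by ln[(1 − m)/(0.5 − m)]/ln 2. This gives 1.17 at m = 10%, 1.42 at 20% and 1.81 at 30%.
- If missed relapses become SAP PD later, at 1 to 4 times the original hazard, a simulated median of about 24 weeks becomes about 25-27 weeks (10% missed), 27-31 (25%) or 29-40 (50%).

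**The case against.** The strongest case is about weight. The sponsor stopped the study for lack of efficacy after the interim futility analysis (SAP 2.3), and SAP 3.5 says no formal comparisons will be done. The interim review has already taken place, so a re-derivation cannot alter it. The same rule applies to both blinded arms, and no bias in the hazard ratio can be derived. SAP Section 6.6, on changes from the protocol, is redacted and may declare or justify the new reference. All of this stands and lowers the stakes. It does not make the endpoint measure loss of response, and SAP 6.4.2 still specifies the full DOR analysis. Non-disclosure is not alleged.

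On the numbers, the protocol's reference is a subject-level category, and it does not say which visit supplies the organ scores when several visits share that category. The counts therefore hold for a given reference visit, and a different choice would change individual classifications. They are unweighted single-organ paths, and the zero for exact return follows by construction. The first set of multipliers assumes no later capture and so sits at the high end. By duration, the taper steps where the steroid criterion is met for certain cover weeks 1-5 of 10, and weeks 1-7 with the ambiguous step. The flare inconsistency depends on how flare worsening is read, and the SAP revision log reports very few flares. These are fair limits on the size; the mismatch and its general direction remain.

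**Conclusion.** The point holds. SAP Table 3 and Protocol Table 8-1 define the event that ends DOR differently. Under the SAP, a sustained return to baseline has no organ-based PD, whereas the protocol ends the response unless the 0 to 1 exemption applies or the organ threshold is not reached (for example, a liver rise below 2 × ULN). Worsening past baseline by the organ threshold, new organ involvement that meets it, return to baseline steroid dose and new systemic immunosuppression still count, so only some relapses are lost. Longer reported DOR is a strong tendency, not a rule for every subject, given the reverse mouth case. Its size cannot be calculated, because neither the share of relapses missed nor a median DOR is given. BORR is essentially unaffected: it takes the best response by 24 weeks, which a later relapse does not undo. This should be fixed, but it does not threaten the primary analysis.

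**What to change.** Keep baseline as the reference for CR, PR and SD and for worsening before first response, so that BORR is unchanged. For DOR, define PD after response as in Protocol Table 8-1: apply the SAP Appendix 2 thresholds against the organ scores at the best overall response to date. State which visit is the reference when several share that category. Write the flare exclusion into the PD criterion itself, and say what flare worsening is measured from. Keep the two therapy-based criteria as they are. Report the baseline-referenced DOR as a sensitivity analysis only.

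The cost is SAP wording and a re-derivation from NCAA scores already collected. No new data are needed. Reported DOR will generally be shorter. The start date of DOR is the same in both documents and is not part of this point.
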